6.6 Patient Diary

The patients will be supplied with a diary at visit 2, 3, 4 and 5 respectively (during the Diamyd and etanercept treatment period).

All patients and their parent(s)/legal guardian(s) will be informed, during etanercept treatment, to carefully follow the patient's general condition, and if affected, to measure the patient's morning

body temperature daily, and in case it is elevated also measure it at least once more that day. The body temperature should be documented in the patient diary.

Since fever is one of the first signs of infection, all patients experiencing fever during the etanercept treatment period should, in addition to contacting medical health care and the study team, continue to measure the body temperature daily and document the temperature in the patient diary.

Note: For safety reasons, during the etanercept treatment, this diary must be collected and reviewed by the investigator at every visit to detect potential side effects of etanercept.

The patient will also be asked to use diary for documentation of injection site reactions from the Diamyd subcutaneous injections during the week following injection.

The patient will carefully be instructed by study personnel on how to complete the diary and the investigator will review these together with the patient at the corresponding visit to sort out any inconsistencies and record any AE/SAE information onto the relevant CRF.

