4.2 Endpoints

4.2.1 Primary endpoints

Primary endpoints:

To Evaluate the tolerability of a combination therapy with Diamyd, Vitamin D and etanercept at Month 6 (main study Period), 9, 15 and 30 (extension study period)

Variables to evaluate tolerability:

- Reactions of the injection site
- Infections
- Occurrence of Adverse Events (AEs)
- Occurrence of Serious Adverse Events
- Physiological and Neurology assessments
- Laboratory measurments (biochemistry and haematology), including Calcium and Vitamin D in serum
- GAD65AB titer (GADA)

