6.10 Concomitant Medication

Any concomitant medication used during the study, whether considered relevant for the study or not by the investigator must be reported on the concomitant medication log of the CRF. Please also see section 8.5, below.

7

7 Scheduling of Procedures Table 2. Pilot EDCR IIa Study, Schedule of Study Events, DIABETES patients

Study Period	Scree- ning	Intervention Main Study Period			Follow-up Extension Study Preiod				
Visit number	1	2	3	4	5	6	7	8	9
Day from Baseline (Visit 2)	D	D1	M1	M2	M3	M 6	M9	M 15	M30
(Day/Month)	-10 to		(D30	(D60	(D90	(D180	(D270	(D450	(D900
	-21		± 3)	± 3)	± 7)	± 7)	± 14)	± 14)	±14)
Informed Consent	Х								
Inclusion/Exclusion Criteria	Х								
Etanercept Administration starts		Start			Stop				
·		Day 1			Day 90				
Vitamin D administration starts		Start Day 1						Stop Day 450	
GAD-Alum (Diamyd) injections			Х	Х					
Medical History	Х								
General Physical Examination	Х					Х	Х	Х	Х
Brief Physical Examination		Х	Х	Х	Х				
Neurological Examination	Х					Х	Х	Х	Х
Concomitant Medication	Х	Х	Х	Х	Х	Х	Х	Х	Х
Weight, height, BMI	Х	Х	Х	Х	Х	Х	Х	Х	Х
Urine pregnancy test (females)	Х	Х	Х	Х	Х	Х	Х	Х	Х
Injection site inspection ^a			Х	Х					
Insulin dose		Х	Х	Х	Х	Х	Х	Х	Х
Self-Reported Severe		Х	Х	Х	Х	Х	Х	Х	Х
Hypoglycemia ^b		[ 						
Adverse Events		Х	Х	Х	Х	Х	Х	Х	Х
Patient Diary review and collection			х	Х	Х	х			
Screening for tuberculosis, including blood tests, medical history and pulmonary X-ray	Х								
Screening for Hepatitis B and C (blood tests)	Х								
Blood sampling for safety			-						
Hematology	Х	Х	Х	Х	Х	Х	Х	Х	Х
Chemistry, including Calcium	Х	Х	Х	Х	Х	Х	Х	Х	Х
Urinalysis									
Microalbuminuria	Х	Х	Х	Х	Х	Х	Х	Х	Х
Creatinine	Х	Х	Х	Х	Х	Х	Х	Х	Х
Blood sampling for Auto-antibod									
GADA	Х	Х	Х	Х	Х	Х	Х	Х	Х
Other diabetes-related		Х	Х	Х	Х	Х	Х	Х	Х
autoantibodies	6	L	L			L		L	L
Blood sampling for Diabetes stat			N/	N N	N/		N/	N/	v
HbA1c	X	X	X	X	X	X	X	X	X
Fasting glucose/C-peptide	Х	X	Х	Х	Х	X	Х	X	X
MMTT glucose/ C-peptide		Х				Х		Х	Х
Blood sampling for genetics						1			
HLA Blood compliant for immunology		Х							
Blood sampling for immunology TNF-alfa, IL-1 beta, IL-2, IL-17,		Х	Х	Х	Х	Х	Х	Х	Х
		^	^	^	^	^	^	^	^
IL-5,10, 13 IFN-gamma and T-regulatory									
IFN-gamma and T-regulatory cells									
IFN-gamma and T-regulatory cells Blood sampling for viruses							X		
IFN-gamma and T-regulatory cells Blood sampling for viruses Enteroviruses ^c		X	Х	Х	X	X	Х	X	Х

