8.3 Dosage and Administration

Etanercept	0.8 mg/kg body weight (max 50 mg) given subcutaneously once weekly from Day 1-90
Vitamin D	2 000 IU per day, given per os from Day 1 to Day 450
GAD-Alum:	$20 \ \mu g$ given subcutaneously in the stomach area two times with one month interval.

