9.1 Assessments

9.1.1 Variables

The tolerability and safety assessments includes occurrence of adverse events (AEs), laboratory measurements, physical examinations and neurological assessments (See section 6.3-6.7)

Adverse events will be recorded by the physician at every visit throughout the study.

Blood tests for safety:

- Chemistry: Creatinine, Calcium, Liver function tests (alanine aminotransferase [ALT], Aspartate Aminotransferase [AST], Alkaline Phosphatase, Bilirubin)
- Haematology (MHC, MCV, MCHC, Hemoglobin, Platelets, Leukocytes)

Urinalysis for safety:

- Urine pregnancy test as appropriate
- Microalbuminuria
- Creatinine

Other Variables which will be evaluated:

- Inflammatory markers, especially TNF-alfa, IL-1 beta, IL-2, IL-17
- Th2-deviation of cell-mediated immune response seen e.g. as increased ratio of IL-5,10, 13 in comparison with IFN-gamma, TNF-alfa, IL-1 beta and IL-17, and increase of T-regulatory cells
- C-peptide (90 minute value and AUC_{mean 0-120 min}) during an MMTT
- Proportion of patients with a stimulated maximum C-peptide level above 0.2 nmol/L
- Fasting C-peptide
- Hemoglobin A1c (HbA1c)
- Exogenous insulin dose per kg body weight and 24 hours
- Vitamin D levels in serum

Outcomes above are in agreement with the general Guidelines for Intervention Trials in subjects with newly diagnosed T1D defined by the Immunology of Diabetes Society (89).

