10.3 Statistical Analysis Plan

In brief the following analysis is planned:

All continuous variables will have the following descriptive statistics displayed: number of observations (n), mean value, standard deviation, minimum, median, and maximum. All variables Confidential

of a categorical nature will be displayed with frequencies and percentages. The tabulation of the descriptive statistics will be split by treatment group and visit. Where appropriate, baseline (screening) descriptive statistics will also be included.

Demographic and other baseline characteristics

Demographics such as age and gender will be described for Intention-to-treat and the Total population. Measures for other baseline characteristics are medical history, current medical conditions (at baseline), and current diabetes medication (at baseline). The baseline characteristics will be presented for the safety population. Demographics and baseline characteristics will be presented using descriptive statistics (summary tables).

Variables:

The AE/SAE data will be presented using a standardized tabulation of the frequency and incidence rate of all observed AEs/SAEs. The frequencies and incidence rates are calculated on a per patient basis. Adverse events will be summarized by body system, causality, and severity. Other safety data will be presented by descriptive statistics. Data regarding C-peptide and immune system as well as Adverse events and other safety data will be summarized descriptively.

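### Capture of AEs and infections changes by period and Section 10.3 has no exposure time, so early-versus-late differences in these primary variables cannot be interpreted

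*Combined protocol and SAP*

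**What the plan says.** Section 4.2.1 makes tolerability the primary endpoint, assessed for Diamyd, "Vitamin D and etanercept at Month 6 (main study Period), 9, 15 and 30 (extension study period"). Its variables include infections, AEs and injection-site reactions.

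The means of finding these events change over the study:

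- **Temperature and fever.** Section 6.6 ties these instructions to etanercept: "all patients experiencing fever during the etanercept treatment period should, in addition to contacting medical health care and the study team", keep measuring and recording temperature. Section 8.3 has etanercept "given subcutaneously once weekly from Day 1-90".
- **Diary.** "The patients will be supplied with a diary at visit 2, 3, 4 and 5 respectively" (Section 6.6). The Table 2 row "Patient Diary review and collection" is ticked at Visits 3 to 6. The diary is also used for "documentation of injection site reactions from the Diamyd subcutaneous injections during the week following injection".
- **Visits.** Tables 1 and 2 place Visits 2 to 9 at Days 1, 30, 60, 90, 180, 270, 450 and 900. Physical examination is brief at Visits 2 to 5 and general from Visit 6.
- **AE recording.** "Adverse events will be recorded by the physician at every visit throughout the study" (Section 9.1.1).

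On analysis, Section 10.3 says: "The tabulation of the descriptive statistics will be split by treatment group and visit". It calculates AE frequencies and incidence rates per patient. It gives no patient-time denominator, no analysis periods and no rule for differences in capture.

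**The concern.** Infection is among the commonest reported side effects of etanercept (Section 2.3), so readers will look closely at how infections and other AEs change over time. The trial has one arm. A reader who asks whether events were commoner during etanercept and GAD-Alum than later has only the patients' own later follow-up to compare with. That comparison mixes any drug effect with two artefacts: the length of the interval before each visit, and the way events in that interval were found.

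The two artefacts pull in opposite directions. Longer intervals collect more events per visit, so a constant true rate can look like worsening. Weaker capture lowers events per unit time, so the same constant rate can look like recovery after etanercept stops. Section 3 says the results will inform the design of a larger Phase II trial, so either misreading could carry forward.

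Injection-site reactions raise a smaller point. Section 4.2.1 names them at Months 9, 15 and 30, but GAD-Alum is injected at Days 30 and 60 and etanercept only to Day 90.

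**Working it through.** The plan states no figure for this point, and Section 10.2 has no power calculation. The day arithmetic uses Tables 1 and 2. Event rates and recall are assumptions, because the documents give neither.

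**1. Gaps and cover.** Nominal gaps between Visits 2 and 9 are 29, 30, 30, 90, 90, 180 and 450 days. With the visit windows, the last is 422 to 478 days.

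- Diary: Day 1 to Day 180, (180 − 1)/(900 − 1) = 20% of follow-up, ending 90 days after etanercept.
- Etanercept, and with it the temperature rule: 89/899 = 10%.
- Vitamin D, to Day 450: 449/899 = 50%.

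**2. Contact frequency.** Contacts per patient-year = 365.25 × visits / days:

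- Days 1-90: 365.25 × 3/89 = 12.3
- Days 90-270: 365.25/90 = 4.1
- Days 270-450: 365.25/180 = 2.0
- Days 450-900: 365.25/450 = 0.8

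First to last is about a 15-fold fall.

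**3. Effect of interval length alone.** Assume a constant true rate r and full capture. The probability of at least one event in an interval of L days is 1 − exp(−r × L/365.25).

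| r per patient-year | 30 days | 90 days (to Month 6 or 9) | 180 days (to Month 15) | 450 days (to Month 30) |
|---|---|---|---|---|
| 0.5 | 4% | 12% | 22% | 46% |
| 1 | 8% | 22% | 39% | 71% |
| 2 | 15% | 39% | 63% | 91% |
| 4 | 28% | 63% | 86% | 99% |

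Per-visit incidence rises steeply with no change in risk. At r = 2, if only half or a quarter of events in the last interval are captured, Month 30 still shows 71% or 46%, above the 15% of a 30-day interval. The expected per-visit count at Months 9, 15 and 30 falls below that of a 30-day interval only if capture drops below 30/90 = 33%, 30/180 = 17% and 30/450 = 7%. Against the 90-day interval ending at Month 6, the thresholds are 100%, 50% and 20%.

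**4. Effect of weaker capture, as an illustration only.** Suppose the chance that an event is reported halves for every h days between the event and the visit, ignoring the diary. The mean captured share over an interval L is (1 − 2^(−L/h)) × h/(L × ln 2). The first interval length is 89/3 = 29.7 days.

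| h (days) | Share, L = 29.7 | Share, L = 450 | Apparent fall in rate per unit time |
|---|---|---|---|
| 30 | 72% | 10% | 7.5-fold |
| 60 | 85% | 19% | 4.4-fold |
| 120 | 92% | 36% | 2.6-fold |
| 365 | 97% | 67% | 1.4-fold |

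**5. The same model, counted per visit.** Captured events are proportional to L × share. For h = 30, 60 and 120, a 30-day interval gives about 22, 25 and 28 captured day-equivalents. The 450-day interval gives about 43, 86 and 160, which is 2.0, 3.4 and 5.8 times as many. So the rate per month falls while the per-visit count rises, from identical data.

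**The case against.** The strongest objection is that no on- versus after-treatment contrast is planned. All analysis is descriptive. Causality is judged for each of the three drugs separately (Section 9.2.4), and AEs are summarised by causality and severity. A split by visit, if applied to AEs, already follows the capture periods: Visits 3 to 5 cover Days 1-90, Visit 6 covers Days 90-180, and Visits 7 to 9 the rest. Later events also do not rest on recall alone. Patients are examined for new conditions, safety bloods and concomitant medication are collected at every visit, SAEs are due within 24 hours of knowledge (Section 9.2.6), and monitors check the CRF against medical records. Further procedures may stand in the Safety Plan that Section 6.7 cites, which is not part of these documents.

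Much of this stands. It confines the point to non-serious AEs and infections and keeps it a reporting matter. It does not supply patient-time or tell a reader that the columns of a by-visit table cover 30 to 450 days. Causality judgements apply to events already found, so they cannot correct for events missed.

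A reader might also draw three stronger conclusions that the documents do not support:

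- *Active capture exists only while etanercept and GAD-Alum are given.* The Visit 5 diary is collected at Visit 6, so the Month 6 interval has diary cover, although Section 6.6 does not say what to record after Day 90.
- *All four primary time points come after treatment.* Vitamin D is part of the regimen and runs to Day 450, so only Month 30 is clearly off all study drugs.
- *Reported events must fall after treatment.* That requires a rate per unit time and a drop in capture. The planned measure is per patient, and by visit it tends to rise.

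**Conclusion.** The concern holds as a gap in analysis and reporting. For AEs and infections, the intensity of capture and the length of the interval both change during follow-up, and Section 10.3 accounts for neither. A difference between early and late frequencies therefore cannot be read as a drug effect, or as its absence, and the direction of bias depends on which measure is tabulated.

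The visit gaps, diary cover and 15-fold change in contact frequency are arithmetic on the protocol's own schedule. The 15% versus 91% contrast assumes 2 events per patient-year and full capture; over 0.5 to 4 events per year it ranges from 4% versus 46% to 28% versus 99%. The recall figures rest on an assumed half-life with no support in the documents. They show only that a constant true rate could appear to fall anywhere from 1.4-fold (h = 365 days, 97% versus 67%) to 7.5-fold (h = 30 days).

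Section 10.3 does not say outright that its by-visit split applies to the AE tables. If AEs are instead pooled over 30 months, the cumulative count cannot fall, but closely and loosely observed time is merged, so the point remains. Laboratory tests, neurological examination, GADA and SAEs lie outside it.

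**What to change.** In Section 10.3:

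1. Report AEs and infections both as patients with an event and as events per patient-month, separately for four periods, with the capture method stated for each:
   - Days 1-90: temperature rule, diary, roughly monthly visits
   - Days 90-180: diary, one visit
   - Days 180-450: visits only, vitamin D the only study drug
   - Days 450-900: one visit, off all study drugs
2. Base any on- versus after-treatment statement on SAEs, severe AEs, and infections with a medical contact or an anti-infective traceable in the medical record or concomitant-medication log.
3. Summarise injection-site reactions over the injection period, including follow-up after the last etanercept and GAD-Alum injections, rather than at Months 9, 15 and 30.
4. If a recall calculation is shown at all, label it an illustration and include the slow-decay case (h = 365 days).

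The cost is SAP wording and extra tables. No visit, treatment or clinical rule changes. The downside is that the cross-period statement rests on fewer events, in a trial of about 20 patients.

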2.3 Risks of Etanercept (Enbrel[®])

Etanercept (Enbrel[®]) is one of the clinically most well-used biologics in the world and is regarded as justified in the treatment of Juvenile Idiopathic Arthritis (JIA) also in children down to 2 years of age.

Etanercept has documented side effects and the most commonly reported side effects are injection site reactions, infections (URI, bronchitis, cystitis and skin infections, reactivation of tuberculosis and other serious infections such as tuberculosis, and opportunistic infections, including invasive fungal infections, listeriosis and legionellosis), allergic reactions, development of autoantibodies, itching, pruritus and fever.

TNF blockers such as etanercept affect the immune system and its use can affect the body's immune response towards infections. Serious infections affect less than 1 of 100 patients that are treated with etanercept. Deadly and life-threatening infections as well as sepsis have been reported. Different kinds of malignancies have also been reported while treated with etanercept,

even if this AE has been questioned by Swedish researchers as the incidence of malignancy in children and adults with rheumatic disorders is increased even without treatment. Additionally hematological, neurological and autoimmune reactions have been reported, including rare cases of pancytopenia (less than 1 of 1000) and very rare cases of aplastic anemia (less than one of 10 000). Central and peripheral demyelination has been reported in both rare and very rare cases. Also, rare cases of lupus and lupus-like syndrome and vasculitis have been reported

There are also reports that the risk for hypoglycemia may increase in patients with diabetes being treated with etanercept.

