6.2 Assessments and Procedures

- 1. Standard insulin treatment, education and psychosocial support for newly diagnosed T1D patients.
- 2. Normalization of fluid, electrolyte and acid-base balance.
- 3. Thereafter information about the study.
- 4. When the patients and parent(s) / legal guardian(s) have given their informed consent, at the latest 100 days after diagnosis, screening is performed with a fasting venous sample from patients who are eligible according to other criteria than C-peptide and GADA concentrations (Visit 1). Patients are also tested for tuberculosis, renal or liver disease at this visit (see section 5.3.1 and 5.3.2 above).
- 5. At Visit 2 (Baseline), Visit 6 (6 months), Visit 8 (15 months) and Visit 9 (30 months), assessment of residual endogenous insulin secretion by MMTT.
- 6. Blood sampling for Vitamin D in serum at Visit 1, and then after one month of treatment at Visit 3 (before the first GAD-alum treatment) and at Visit 8 (15 months)
- 7. HbA1c, safety (haematology and chemistry), autoantibody titres (GAD65, IA-2), immunology are followed by blood samples at every visit.
- 8. Exogenous insulin dose/24 hours, AEs and concomitant medication are registered at every visit.
- 9. Self-reported hypoglycaemia (defined as needing help from others and/or seizures and/or unconscious) registered at every Study Visit.
- 10. Any symptoms or signs of other medical problems should be treated at the discretion of the clinical doctor. Thus if a patient experiences symptoms and/or signs of infection that should be treated lege artis.

Examinations will be performed according to table 2 in Section 7 below, and in the order outlined in the case report form (CRF).

6.2.1 All Visits, Visit 1 through 9

Note that the patient should attend all study visits in the morning following an overnight fast (> 10 hours, water allowed).

For patients with evidence of an infection (including fever), the complete visit should be postponed for 5 days or until the patient has recovered.

6.2.2 Injections with GAD-Alum (Diamyd), Visits 3 and 4

Injections of GAD-alum (Diamyd) will be administered at Visits 3 and 4, subcutaneously in the stomach area.

After the injection, the patient shall remain in the vicinity of the study site for the next hour, and the injection site will be examined by investigator/study nurse 1 hour post injection.

6.2.3 Mixed Meal Tolerance Test (MMTT), Visits 2, 6, 8 and 9

The MMTT must be performed according to the instructions in the CRF.

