6.5 Physical Examination and Neurological Examination

At the screening visit (Visit 1) the patient will undergo a general physical examination and a neurological examination and any findings will be reported as pre-existing conditions on the Medical History CRF page.

During the subsequent study visits the patient will be examined for any new medical conditions or worsening of the pre-existing ones. Any change in pre-existing conditions or new conditions must be entered on the AE page in the CRF and any medication given on the concomitant medication pages.

The patients will, in addition to the physical examinations by the physician, undergo a standardized clinical neurological examination at 0, 6, 9, 15 and 30 months. The neurological tests are performed in order to detect possible mild signs of neuromuscular disease such as disturbance of strength, balance, and coordination.

The neurological examination includes:

- Extremity reflexes
- Romberg (balance and coordination)
- Walk on a line, 2 meters (balance and coordination)
- Standing on 1 leg, left and right, 15 seconds per leg (balance and coordination)
- Finger-nose (coordination)
- Mimic (cranial nerves)
- Babinski reflex (central function)
- Muscle strength (shake hands) biceps, triceps, distal extensors, and flexors

These examinations may also be repeated between scheduled visits at the discretion of the investigator. Screening for neurological disease with electroencephalogram (EEG) is not included due to low sensitivity and specificity. However, if any signs of neurological dysfunction are detected, the patient should be referred to a neurologist for further evaluation.

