IFN-gamma and T-regulatory cells Blood sampling for viruses Enteroviruses ^c Blood sampling additional		-				-			
IFN-gamma and T-regulatory cells Blood sampling for viruses Enteroviruses ^c	X	X	X X X	X	X	X X X	X X X	X X X	X

^a Inspection of injection site before and 60 minutes after GAD-Alum injection by investigator or nurse

^b Severe Hypoglycemia is defined as needing help from others and/or seizures and/or unconscious
 ^c Especially certain types of Coxsackie virus may play a role for the beta cell destruction. Details will depend

on results in the ongoing DIABGAD trial.

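### Injection-site reactions are a primary tolerability variable, but the protocol text asks for them specifically only after GAD-Alum; weekly etanercept relies on general adverse event collection

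*Combined protocol and SAP*

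**What the plan says.** Section 4.2.1 opens its list of tolerability variables with "Reactions of the injection site". The variable belongs to the combination and names no product.

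The site-specific methods in the text all concern GAD-Alum:

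- Section 6.2.2, on the GAD-Alum injections at Visits 3 and 4: "the injection site will be examined by investigator/study nurse 1 hour post injection".
- Section 7, Table 2, footnote a: "Inspection of injection site before and 60 minutes after GAD-Alum injection by investigator or nurse".
- Section 6.6: patients use the diary for "documentation of injection site reactions from the Diamyd subcutaneous injections during the week following injection".

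On etanercept, Section 2.3 says that "the most commonly reported side effects are injection site reactions", followed by infections and other events. Sections 8.1 and 8.3 give it subcutaneously once a week from Day 1 to Day 90. The only diary entry that Section 6.6 specifies for the etanercept period is temperature: "The body temperature should be documented in the patient diary". The same section adds that "this diary must be collected and reviewed by the investigator at every visit to detect potential side effects of etanercept". Section 10.3 reports adverse events descriptively, with rates per patient.

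**The concern.** Tolerability of the combination is the primary question of an uncontrolled pilot of about 20 patients, and Section 3 says the results will inform a larger Phase II trial. With no comparator and purely descriptive reporting, the observed proportion with a site reaction depends directly on how completely reactions are collected.

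The text asks a targeted question after the product given twice and none after the product given weekly. A family that follows Section 6.6 literally writes down Diamyd site reactions and temperatures, and could reasonably conclude that a sore etanercept site needs no entry. If some patients' mild reactions go unmentioned, the error runs in one direction: the combination looks better tolerated at the injection site than it was.

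**Working it through.** The protocol gives no figure to reproduce: Section 10.2 states that no formal power analysis was done, and no site-reaction rate is quoted. The check is a comparison of the text by product, a count from the schedule, and a look at how the per-patient rate behaves.

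**1. Collection routes, by product**

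| Route | GAD-Alum | Etanercept |
|---|---|---|
| Site inspection before and 60 minutes after (6.2.2, Table 2) | Yes | Not specified |
| Diary item on site reactions, one week (6.6) | Yes | Not specified |
| Adverse events registered at every visit (6.2 item 8, 9.1.1), mild ones included (9.2.3, 9.2.5) | Yes | Yes |
| Diary reviewed together with the patient (6.6) | Yes | Yes, expressly for etanercept side effects |
| Examination for new conditions (6.5; brief examination at Visits 2-5, Table 2) | Yes | Yes |
| Active collection of adverse events during etanercept treatment (6.7.1) | No | Yes |
| Staff and family education on side effects (6.7) | Yes | Yes |
| Stopping criteria that mention reactions to the product (5.4) | No | Allergic reactions, urticaria and severe reactions only |

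**2. Injection count** (assumes a first dose on Day 1, exact 7-day spacing and full compliance)

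Etanercept on Days 1, 8, 15, ..., 85 is 13 doses. GAD-Alum on Days 30 and 60 is 2. So 13/15 = 87% of injections have no site-specific item in the text. This measures coverage, not bias. Two etanercept doses (Days 36 and 64) fall inside the Diamyd diary weeks, but the diary sentence asks only about Diamyd.

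**3. Timing against visits**

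Days from each dose to the next visit (Days 30, 60, 90): 29, 22, 15, 8, 1; 24, 17, 10, 3; 26, 19, 12, 5. Ten of 13 exceed 7 days. Visits 3, 4 and 5 fall 1, 3 and 5 days after a dose, so some reactions will be seen. Across the visit windows in Section 7.1 these become 0-6, 0-6 and 0-12 days, and 7 to 11 doses fall more than 7 days before the next visit.

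**4. What a missed reaction does to the rate**

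Rates are per patient, so one recorded reaction is enough. Let p be the risk of a site reaction per etanercept dose, r the chance that a reaction to one of the 10 doses farther from a visit is recorded (the 3 nearest always are), and g the share of patients with a recorded GAD-Alum site reaction. All three are assumptions; the documents give none of them. Independence is assumed throughout.

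- Etanercept only, true: 1-(1-p)^13
- Etanercept only, recorded: 1-(1-p)^3 × (1-rp)^10
- Shortfall in the combined per-patient rate: (1-g) × (etanercept-only shortfall)

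With p = 5%, **etanercept only**: true 1-0.5133 = 48.7%. Recorded with r = 0.5: 1-0.8574×0.7763 = 33.4%, a shortfall of 15.2 points. Recorded with r = 0.75: 1-0.8574×0.6824 = 41.5%, a shortfall of 7.2 points.

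**Combined rate**, same inputs:

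| g (assumed) | Shortfall, r = 0.5 | Shortfall, r = 0.75 |
|---|---|---|
| 25% | 11.4 points | 5.4 points |
| 50% | 7.6 points | 3.6 points |
| 75% | 3.8 points | 1.8 points |

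In 20 patients this runs from 0.114×20 = 2.3 down to 0.018×20 = 0.4 patients. With r = 1 the shortfall is zero. It is also zero if patients who react do so at every dose. The table shows how the rate responds to the assumptions and is not an estimate for this trial.

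**The case against.** The strongest reply is that the general routes are not passive. Section 6.7.1 tells the team to collect adverse events actively during etanercept treatment, Section 6.6 has the investigator go through the diary with the patient, and Section 6.5 says "During the subsequent study visits the patient will be examined for any new medical conditions or worsening of the pre-existing ones". Section 6.7 adds that the Safety Plan ensures staff know the side effects and families are told of them. All of this stands. A reader might infer that etanercept site reactions go uncollected, or arrive only by chance report; the documents do not support that. What remains is that none of these routes names the etanercept injection site.

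A reader might also infer from the timing that most doses pass without staff contact. The documents do not settle this. The sentence in Section 8.2 placing all dosing in hospital sits in the GAD-Alum paragraph, and exclusion criterion 16 requires an on-site pregnancy test within 24 hours before etanercept for menstruating females. Where the weekly doses are given is otherwise not clearly stated.

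Nor do the documents support calling under-recording likely, or giving it a size: they contain neither reaction nor reporting rates. Percentages for etanercept alone would overstate the loss in the combined rate whenever g is above zero, and Section 2.2 confirms that GAD-Alum site reactions occur.

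Finally, closer follow-up of the unapproved product is reasonable and no comparison between products is planned, so unequal collection is not a fault in itself. The point concerns only how complete the combined rate is.

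**Conclusion.** The point holds in a limited form. For a primary tolerability variable, the protocol text has a site-specific item for 2 of about 15 injections per patient and leaves the other 13 to general adverse event collection. Mild, short-lived etanercept site reactions may be recorded less completely, and any resulting error would favour the combination.

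The size cannot be computed. In the combined per-patient rate the shortfall is the etanercept-only shortfall times (1-g), with g unknown and independence assumed. Confidence is medium, because the diary form, CRF and Safety Plan were not available and any of them may already close the gap. This is an inexpensive improvement to consider, not a flaw that undermines the trial.

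**What to change.** In Section 6.6, extend the existing diary sentence so that patients record site reactions after each etanercept injection as well as after Diamyd, noting which injection each reaction followed. If the diary form, CRF or Safety Plan already has such an item, cite it in Section 6.6 instead.

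In Section 10.3, report the per-patient proportion with any injection-site reaction, overall and by attributed product. Section 9.2.4 already has causality judged separately for each treatment, so no new assessment is needed. If collection stays unequal, say so in the study report.

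The cost is about one diary line a week for 13 weeks, in a diary already handed out at Visits 2 to 5, and one small table. No visit, procedure or treatment rule changes. The reported rate may rise.
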